14.0 Potential Benefits to Participants

14.1 Potential Benefits:

As the intervention involves using a smoking cessation app, participants could benefit from using the app and quitting smoking. This benefit is not guaranteed.

15.0 Statistical Considerations

15.1 Data Analysis Plan:

No blinding of the investigative team will occur.

General Approach

All statistical analyses will be performed using SAS (version 9.4) or R (latest version, R Core Team). All statistical tests will be two-sided and a significance level of 0.05 will be used. Proper transformation such as the logarithm transformation will be used to approximate normality for

MEDICAL PROTOCOL (HRP-590)

PROTOCOL TITLE: QuitGuide for American Indians: Aims 2 & 3

VERSION DATE: 11-16-2022

the outcome variables. All analyses will be completed using intent-to-treat principle unless otherwise noted.

Describing the Study Population

Baseline characteristics will be summarized for all participants and by study arm to identify any treatment group imbalances post-randomization. This will include household income, education level, traditional tobacco use, cultural identity, multiple tobacco use, quit readiness, nicotine dependence and CPD. Continuous variables will be summarized using mean, standard deviation, median and range, and compared between study arms using Student's t-tests or Wilcoxon rank-sum tests, as appropriate. Categorical variables will be summarized using frequency and percentage, and compared between study arms using Chi-square or Fisher's exact tests, as appropriate.

Primary Endpoint Analysis

The primary endpoint is the frequency of app use initiated by the participant. The number of times the app is initiated per day will be measured using data from Smokefree.gov. If a participant does not use the app on a particular day, Smokefree.gov records this as non-use or 0 for that day. The total number of times will be summarized for analysis by totaling the number of times the app is initiated from randomization to 5 weeks post-randomization.

Primary Analysis

The objective of our primary analysis is to test the treatment effect on frequency of app initiated by the participant. Frequency of app initiated will be summarized by treatment group (tailored app vs standard app) using descriptive statistics, and analyzed using a Poisson regression model with covariates for treatment group and the three stratification factors (rural/urban clinic, male/female gender and <50 years of age/50+ years of age). Assumptions about mean and variance will be evaluated and if over-dispersion is present, negative binomial regression will be used. If data are zero-inflated, zero-inflated Poisson or negative binomial models may be considered.. This analysis will be performed using data for all participants who were randomized, while assuming non-use of app for those who did not complete the week 5 survey from the last day they launched the app.

Secondary Analysis

A secondary analysis of the primary endpoint will be performed that also adjusts for any other covariates that differ across treatment groups at baseline with a p-value less than 0.20 (covariates listed above). We acknowledge the limitations of this due to a small sample size and will take this into account when determining what additional covariates to adjust for. Additionally, a sensitivity analysis will be performed for all subjects who completed the week 5 survey.

Secondary and Exploratory Endpoint Analysis

Secondary and exploratory endpoints will be analyzed using the same approach as the primary endpoint. These endpoints will be analyzed using an appropriate regression framework (i.e. linear, logistic, Poisson etc.), adjusting only for baseline measurements of the endpoint, if available, and the three stratification factors (rural/urban clinic, male/female gender and <50 years of age/50+ years of age). Secondary analyses will consist of an adjusted analysis, as

MEDICAL PROTOCOL (HRP-590)

PROTOCOL TITLE: QuitGuide for American Indians: Aims 2 & 3

VERSION DATE: 11-16-2022

described above. All analyses will utilize residual plots and other diagnostic statistics to evaluate all modeling assumptions.

Measures of the ability to abstain from smoking (self-reported 24-hour, 7-day and 30-day abstinence) will be analyzed using a similar approach to the primary and secondary/exploratory endpoints, and summarized using a binary endpoint. Continuous 7-day biochemically-verified abstinence (saliva cotinine < 10 ng/mL⁸) will be summarized for those who self-reported 7-day abstinence prior to the week 5 survey, and analyzed using logistic regression, with a main effect for treatment group and adjustment of the stratification factors (rural/urban clinic, male/female gender and <50 years of age/50+ years of age). Because traditional tobacco (depending on the method of use and plants used) and secondhand smoke can increase saliva cotinine, additional analyses may be performed to explore their impact on biochemically-confirmed abstinence. In addition, secondary analyses will consist of an adjusted analysis, as described in above.

Subgroup Analysis

No subgroup analyses will be performed due to small sample size.

Missing Data

An intent-to-treat analysis requires that subjects are analyzed according to their randomized treatment assignment, regardless of compliance to the study product, and that complete data are available on all study subjects. Every effort will be made to limit the amount of missing data in this trial, and study participants will be incentivized to partake in each study component, return the saliva sample, and complete all components.

We will compare subjects with and without missing data in order to identify baseline covariates associated with missing data. All observed data will be utilized in the analyses, with missing data being assumed to be missing at random. Sensitivity analyses of the secondary/exploratory endpoints using multiple imputation may be considered depending on the amount of missingness.

Interim Analyses

No planned interim analyses.

All statistical analyses will be performed by [name] from the Masonic Cancer Center, Biostatistics Core.

15.2 Power Analysis:

Our sample size is based on the primary outcome, frequency of app use initiated by the participant during the 5-week period. Using a two-sided, two-sample test for Poisson rates, a total of 116 participants (n=58 in the tailored group and n=58 in the non-tailored group) will allow us to achieve 80% power to detect a difference in frequency of app use between the groups of 3.15 assuming a rate of 35 (1 time per day over the 5 weeks) in the non-tailored group and an alpha of 0.05. This sample size is in alignment with other mHEALTH-related smoking cessation feasibility studies.^{36, 50}

15.3 Statistical Analysis:

See above.

MEDICAL PROTOCOL (HRP-590)

PROTOCOL TITLE: QuitGuide for American Indians: Aims 2 & 3

VERSION DATE: 11-16-2022

15.4 Data Integrity:

PI will periodically check for completeness as well as outliers or unusual values

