4. **Exit Survey:** At the end of the day on the last day of the 5 weeks of app use (i.e., 5 weeks + 1 day), an automated survey link from REDCap will be sent to participants email to assess self-report outcome measures. Participants will also be called and texted to remind them to complete the survey.
5. **Optional end of study interview:** Those randomized to the tailored QuitGuide may be asked to participate in a follow-up interview to get their feedback on using the app. We expect asking up to 10 people to complete this interview.

All measures are displayed in the table:

Baseline survey collected via REDCap: Demographics, America Indian Identity Measures, Internet and smartphone use, Traditional Tobacco Use, Commercial Tobacco History, Nicotine Dependence Scale, Contemplation Ladder, Environmental Smoke Exposures, Health Literacy, Alcohol consumption, Financial Strain, Perceived Stress Scale, Brief Resilience Scale, Everyday Discrimination Scale
--

Data collected through using app and transferred from SmokeFree.gov:

All app user data. Any and all interactions with the app including days and frequency of use each day and which app components are accessed.
--

MEDICAL PROTOCOL (HRP-590)

PROTOCOL TITLE: QuitGuide for American Indians: Aims 2 & 3

VERSION DATE: 11-16-2022

Exit survey collected via REDCap: Contemplation Ladder TimeLine follow-back calendar to assess self-report CPD, use of any pharmacotherapy, 24-hour quit attempts, use of other cessation resources, Minnesota Nicotine Withdrawal Scale, Usability of App Design by System Usability Scale (SUS) Acceptability measures; plus open-ended responses on app
Audio recordings from the interviews among a subset of the participants
Saliva Sample

5.3 Study Duration:

- Individual participant duration is 5 weeks.
- The duration to enroll all study participants is 1.5 years.
- The duration for all data collection and analysis is 2.5 years.

5.4 Use of radiation:

The study does not use any radiation.

5.5 Use of Center for Magnetic Resonance Research:

The study does not use any CMMR resources.

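### Baseline internet and smartphone use is collected but not pre-specified as a covariate for the app-use endpoint, so the trial may forgo a little precision that would cost little to obtain

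*Combined protocol and SAP*

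**What the plan says.** The measures table in Section 5.2 opens the baseline survey with "Demographics, America Indian Identity Measures, Internet and smartphone use", so the variable will be in hand before randomization.

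The primary endpoint (Sections 3.1 and 15.1) is the total number of times the participant launches the app from randomization to 5 weeks. Section 15.1 analyses it with a "Poisson regression model with covariates for treatment group and the three stratification factors" (rural/urban clinic, gender, age under or over 50). It moves to negative binomial regression if there is over-dispersion and allows zero-inflated models.

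A secondary analysis of the same endpoint adds covariates that differ between arms at baseline with p below 0.20, and points back to the list given for the baseline description: "This will include household income, education level, traditional tobacco use, cultural identity, multiple tobacco use, quit readiness, nicotine dependence and CPD". That list has eight entries. Internet and smartphone use is not one of them.

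**The concern.** The outcome is a count of launches of a smartphone app. Of the baseline variables collected, general internet and smartphone use looks closest in content to it, and heavier phone users may well open any app more often. If so, that difference between people stays in the residual variation of the primary model and widens the interval for the arm comparison. The data are already being collected, so using them requires no extra participant contact.

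The adjusted analysis is unlikely to make up for this. Its named list omits the variable, and entry depends on chance imbalance between arms rather than on how well a variable predicts use. At stake is the width of the primary interval, not bias or the validity of the test.

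**Working it through.** **1. The plan's own figure.** Section 15.2 plans on "Using a two-sided, two-sample test for Poisson rates" with 58 per arm, "assuming a rate of 35 (1 time per day over the 5 weeks) in the non-tailored group and an alpha of 0.05", and a difference of 3.15, so the tailored rate is 35 + 3.15 = 38.15.

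- Standard error of the difference: √((35 + 38.15)/58) = √1.2612 = 1.123.
- Power: Φ(3.15/1.123 − 1.96) = Φ(0.845) = 80.1%.
- Required n per arm: 73.15 × (1.960 + 0.842)² / 3.15² = 57.9, so 58.

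The stated 80% with 116 participants reproduces.

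**2. Adding a baseline predictor.** For a negative binomial count with dispersion k, the variance of the log rate ratio is

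V = [(1/35 + k) + (1/38.15 + k)] / 58.

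If the covariate explains a share r of the between-person dispersion beyond the stratification factors, replace k with k(1 − r). The standard error is multiplied by √(V with covariate / V without), and the equivalent sample size is 116 × (V without / V with). The documents give neither k nor r, so both are assumptions.

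Example with k = 0.5 and r = 10%: 1/35 + 1/38.15 = 0.0548. Without the covariate the bracket is 0.0548 + 2 × 0.50 = 1.0548. With it, 0.0548 + 2 × 0.45 = 0.9548. The ratio is 0.9052, its square root is 0.951, and 116/0.9052 = 128.1.

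Cells show the standard error multiplier and the equivalent total sample size:

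| k | r = 0 | r = 5% | r = 10% | r = 20% |
|---|---|---|---|---|
| 0 (plan's Poisson assumption) | 1.000; 116 | 1.000; 116 | 1.000; 116 | 1.000; 116 |
| 0.1 | 1.000; 116 | 0.980; 120.7 | 0.960; 125.9 | 0.918; 137.6 |
| 0.5 | 1.000; 116 | 0.976; 121.8 | 0.951; 128.1 | 0.900; 143.1 |
| 1 | 1.000; 116 | 0.975; 121.9 | 0.950; 128.5 | 0.897; 144.0 |

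At k = 0, people in the same arm and stratum share one launch rate, so a covariate has no between-person variation to explain.

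**3. In terms of power.** At k = 0.5, an effect with 80% power without the covariate (rate ratio about 1.46) would have 81.9%, 83.8% or 87.6% at r = 5%, 10% or 20%.

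The planned effect is much smaller: 38.15/35 = 1.09. There, power is Φ(ln 1.09/√V − 1.96). At k = 0.5, √V = √(1.0548/58) = 0.1349, so power is Φ(0.0862/0.1349 − 1.96) = 9.3%. With the covariate it is 9.6%, 9.9% or 10.6% at the same three values of r. At k = 0.1 it is 25.5% without and 26.3%, 27.2% or 29.3% with.

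**4. Cost if the variable is irrelevant.** In a rough simulation (400 trials per setting, lognormal person effects, negative binomial fit, r = 0), adding the covariate moved the rejection rate from 91.3% to 90.8% in one setting and from 83.3% to 81.5% in another. These are differences of 2 and 7 trials in 400. The Monte Carlo standard error of a single rate near 83% is √(0.83 × 0.17/400) = 1.9 points, so no loss is detectable. Only the comparison with and without the covariate is used here, not the level of power.

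**5. Adding it to the list only.** Randomization makes any baseline difference a chance one, so a test at p < 0.20 admits a given variable about 20% of the time, and then only to the secondary analysis.

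**The case against.** The strongest case against is that the benefit is assumed. The documents report no association between phone use and app launches, and under the plan's own Poisson assumption the gain is zero. A reader might infer that the trial is certainly giving up free precision, or that phone habits are a main source of noise. Neither is supported. What weakens the zero-gain argument is that Section 15.1 itself provides for over-dispersion and so does not rely on k = 0 for its analysis.

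Some of the variation is already handled. Section 2.3 relates smartphone ownership to location (71% rural, 81% urban) and education (66% at the lowest level). Rural/urban and age group are in the primary model, and education is on the list for the adjusted analysis. Eligibility also requires a smartphone and sufficient data, which removes the low end of the scale. This stands, and it is why r is defined as variation beyond the stratification factors and why small values deserve the most weight.

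A reader might infer that no model can include the variable. That is too strong. The list is introduced in wording that is not explicitly exhaustive, and the plan keeps some discretion over additional covariates, though the cross-reference does point to the named list.

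A reader might also see an inconsistency, because secondary and exploratory endpoints are adjusted for their baseline values where available. There is none: the app is downloaded after randomization, so launches have no baseline value, and a survey item on phone use is not one.

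Finally, a model with only the stratification factors is coherent for a small feasibility trial. That is correct, and it limits the point to a suggestion.

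**Conclusion.** The point holds as a low-severity, inexpensive improvement. A plausible predictor of the primary endpoint is collected, is absent from the primary model and is not named for the adjusted analysis.

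The gain runs from nothing (no over-dispersion, or no association) to a standard error about 2%, 5% or 10% smaller if the variable explains 5%, 10% or 20% of between-person variation at k of about 0.5. The equivalent sample sizes are about 122, 128 and 143 instead of 116. Both k and r are assumptions, and the documents describe neither the survey items nor their scoring.

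It would be wrong to read this as a remedy for power. At the planned difference of 3.15 with k = 0.5, power is between 9% and 11% with or without the covariate. The unsized over-dispersion is a separate and much larger matter. Leaving the variable out biases nothing and invalidates no test.

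**What to change.** Before any outcome data are seen, define one internet/smartphone-use measure from the existing baseline items, choosing an item that varies among people who all own a smartphone. In the Section 15.1 primary model, pre-specify it as a fourth covariate beside the three stratification factors, regardless of baseline balance, with missing values set to the overall mean. Keep the current model with stratification factors only as a sensitivity analysis. Adding the variable only to the list for the adjusted analysis would achieve little, for the reason in step 5 of the working.

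The cost is one degree of freedom and the work of choosing and documenting the measure in advance. Timing matters because Section 15.1 states that the investigative team is not blinded, so a covariate chosen after outcomes are visible would be less credible.

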5.0 Procedures Involved

5.1 Study Design:

This is a two-arm randomized clinical trial of the tailored vs standard QuitGuide app conducted.

5.2 Study Procedures:

To test feasibility, acceptability, and preliminary efficacy of the tailored QuitGuide versus standard QuitGuide for smoking cessation among AI peoples.

1. **Telephone Screener:** We will recruit AI smokers interested in quitting. Individuals will be screened over the phone for eligibility.

MEDICAL PROTOCOL (HRP-590)

PROTOCOL TITLE: QuitGuide for American Indians: Aims 2 & 3

VERSION DATE: 11-16-2022

2. **Phone-Based Baseline Interview:** If eligible, then consent will be completed. Then, participants will complete a REDCap survey (titled Baseline Survey—see below for measures). Participants will be randomized to either the *Tailored QuitGuide app* or the *Standard QuitGuide app*. Participants will be provided instruction on how to download the app to their smartphone. Upon download, all participants will be asked to provide a unique participant app ID in the app.

Randomization: Participants will be randomized with equal probability to either a tailored version of the NCI QuitGuide or a standard version of the NCI QuitGuide. Randomization will be stratified by rural/urban clinic, male/female gender, and <50 years of age/50+ years of age. Randomization will be completed using permuted block randomization with random block sizes of 2 and 4. We anticipate no or minimal block effects in our data, and therefore, we will not account for block effects in our data analysis. The randomization schedules will be created in advance.

3. **App interaction:** Upon opening the app for the first time, participants will be asked to set a quit date. All participants will set their quit date for one week later to standardize pre- and post- quit times. If smoking relapse occurs, participants will be provided the option to reset the quit date as this flexibility is permitted in the QuitGuide. Each participant will be asked to use the app for 5 weeks. Participants will have the option to contact the research coordinator at any time to report issues. At week 4, participants will be mailed a letter reminding them of the exit survey and will provide routine saliva sample collection kit with instructions to provide the sample on the same day of their exit survey, and materials (e.g., pre-paid envelope) to return the sample to the University of Minnesota for analysis.

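### The primary analysis may switch to a zero-inflated model with no criterion and no named contrast, and the secondary adjusted analyses choose covariates by baseline p<0.20

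*Combined protocol and SAP*

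**What the plan says.** Section 15.1 forms the primary endpoint by "totaling the number of times the app is initiated from randomization to 5 weeks post-randomization". On the analysis set it states: "This analysis will be performed using data for all participants who were randomized". Section 15.2 powers the trial on the same quantity: "80% power to detect a difference in frequency of app use between the groups of 3.15 assuming a rate of 35", with 58 participants per arm.

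The planned model is Poisson regression on arm and the three stratification factors. Negative binomial regression replaces it if over-dispersion is found. A further option follows: "If data are zero-inflated, zero-inflated Poisson or negative binomial models may be considered". No test, threshold or information criterion is attached to it. The text does not say whether arm enters the count part, the zero part or both, or which result decides the primary test. Section 15.1 also calls for residual plots and diagnostics in all analyses, but sets no decision rule, and it states that the investigative team is not blinded.

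Section 5.2 places randomisation before installation: "Participants will be provided instruction on how to download the app to their smartphone".

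For covariates, the secondary analysis of the primary endpoint "adjusts for any other covariates that differ across treatment groups at baseline with a p-value less than 0.20", drawn from eight baseline variables listed in Section 15.1. Because the sample is small, the team "will take this into account when determining what additional covariates to adjust for". The adjusted analyses of secondary and exploratory endpoints follow the same approach.

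**The concern.** Participants receive the app after randomisation, so someone who never opens it is a genuine zero on the endpoint. For a trial of feasibility and acceptability, failure to take up the app is part of the answer.

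Poisson and negative binomial regression with a log link both estimate the ratio of mean total launches, so moving from one to the other keeps the question. A standard zero-inflated model splits the data into a latent class that never uses the app and a count distribution for everyone else. Its count coefficient compares use among potential users and leaves out any arm difference in uptake. An unblinded team could therefore reach a primary test that no longer addresses total use, with nothing in the plan to say whether the count part, the zero part or a combined quantity decides.

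The p<0.20 rule is a separate and smaller matter. After randomisation, baseline differences arise by chance. The rule therefore picks covariates by chance imbalance, whatever their prognostic value, and the adjusted model cannot be known in advance.

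**Working it through.** **1. The plan's own figure.** Inputs from Section 15.2: rates 35 and 35 + 3.15 = 38.15, 58 per arm, two-sided alpha 0.05.

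Power = Φ(3.15 / √((35 + 38.15)/58) − 1.96) = Φ(2.805 − 1.960) = 0.801.

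The stated 80% is reproduced, and it concerns the overall mean rate.

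**2. Two different effects.** Let p0 and p1 be the never-use shares and m0 and m1 the mean launches among users (0 = standard, 1 = tailored).

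- Total ratio = (1 − p1)m1 / ((1 − p0)m0)
- Count ratio = m1 / m0

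These agree only when p0 = p1. With m0 = m1 = 35 and never-use 30% vs 10%, the total ratio is 0.90/0.70 = 1.29 while the count ratio is 1.00. With never-use 10% vs 30% and 35 vs 45 launches among users, both totals are 0.9 × 35 = 0.7 × 45 = 31.5, so the total ratio is 1.00 while the count ratio is 45/35 = 1.29.

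**3. Consequence for the test.** The never-use shares and the dispersion are assumptions, because the documents give neither. The simulation used 2,000 trials per case, 58 per arm, no covariates, and variance = mean + 0.8 × mean² among users. It compared a robust test of the ratio of mean totals, a Wald test of the zero-inflated negative binomial (ZINB) count coefficient with arm in both parts, and Fisher's test on zero totals. Simulation error near 5% is about √(0.05 × 0.95/2000) = 0.5 percentage points.

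| Never-use, standard vs tailored | Launches among users | Count ratio | Total ratio | Mean ratio rejects | ZINB count rejects | Fisher on zeros rejects |
|---|---|---|---|---|---|---|
| 10% vs 10% | 35 vs 35 | 1.00 | 1.00 | 5% | 5% | 3% |
| 5% vs 2% | 35 vs 35 | 1.00 | 1.03 | 5% | 4% | 3% |
| 10% vs 5% | 35 vs 35 | 1.00 | 1.06 | 7% | 6% | 9% |
| 20% vs 10% | 35 vs 35 | 1.00 | 1.13 | 9% | 6% | 21% |
| 30% vs 10% | 35 vs 35 | 1.00 | 1.29 | 23% | 6% | 67% |
| 40% vs 10% | 35 vs 35 | 1.00 | 1.50 | 42% | 5% | 95% |
| 10% vs 20% | 35 vs 39.4 | 1.13 | 1.00 | 6% | 11% | 22% |
| 10% vs 30% | 35 vs 45 | 1.29 | 1.00 | 6% | 27% | 66% |

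At dispersion 1.25 the 40% vs 10% case gives 30%, 5% and 91%.

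A separate simulation at dispersion 0.25 (10,000 trials per case, with a test among positive counts standing in for the count part) shows the same pattern. With never-use 20% vs 5% and equal use among users, the mean ratio rejects in 27% and the count part in 6%. With never-use 5% vs 20% and equal totals, they reject in 5% and 38%.

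**4. If either part could count as the primary result.** Two independent tests at 0.05 give 1 − 0.95² = 0.0975. The dispersion-0.25 simulation with no arm difference and 20% never-use gives 10.4% for either part, against 5.1% for the single mean-ratio test.

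**5. Covariate rule.** With eight candidates and no true imbalance, 8 × 0.20 = 1.6 are expected to pass. The chance of at least one is 1 − 0.8⁸ = 0.83 if they are independent. Simulation (20,000 trials) gives 0.81 with three correlated pairs (r 0.4 to 0.6) and 0.78 if all correlations are 0.3.

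**The case against.** The strongest reply is that never-use may be rare and the fallback may never be invoked. Section 5.2 puts download instruction in the baseline interview and asks for an app ID on download, and a quit date is set at first opening. Any arm difference in never-use would have to arise before participants see app content. The table supports this line: where never-use is low, or the gap is 10 points or less, the tests differ by at most about 5 percentage points. Clear divergence needs gaps of 20 to 30 points, which no document supports, and a gap that large would show in the zero part and in the descriptive summary. The binding path is Poisson then negative binomial, the stated objective is the effect on frequency of use, and a zero-inflated fit can be marginalised to total use.

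Much of this stands, and it is why the point is conditional. But the text does not guarantee installation during the call. Section 4.1 says the tailored app is not publicly available while the standard one is, so the installation route may differ by arm; the documents do not say whether it does. The stated objective also does not settle which part of a zero-inflated model would be tested, and nothing in the plan requires marginalising.

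On covariates, the candidates are listed in advance, some are plausibly prognostic, the small-sample limitation is acknowledged, and only secondary analyses are affected. All of that is correct. It limits the weight of the point but does not make selection on baseline p-values a good rule.

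**Conclusion.** Both parts hold. The plan allows its primary analysis to move to a model whose usual coefficient answers a different question, without saying when to move or what to test. The effect is negligible if few participants never launch the app or the shares are similar across arms. It becomes material at gaps of about 20 points or more: 23% vs 6% rejection when total use differs only through uptake, and 27% vs 6% in the other direction when totals are equal. These sizes rest on assumed never-use shares, an assumed dispersion and unadjusted simulations.

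The p<0.20 rule costs efficiency and prespecification in the secondary analyses. It does not touch the primary model or inflate its type I error.

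The wording should be corrected before analysis. Confidence that it will matter in practice is moderate, because the never-use shares are unknown.

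**What to change.** State one primary model in Section 15.1: log-link negative binomial regression of the 5-week total in all randomised participants, with arm and the three stratification factors, robust standard errors with a small-sample correction, and the ratio of mean total launches as the single primary contrast. The plan already moves to this model under over-dispersion, so this makes it final. In a check of the adjusted model, HC1 errors gave type I error of about 6% to 7.5%, so a stronger correction such as HC3 is advisable and should itself be checked at this sample size. Report the percentage never using the app and any zero-inflated model as supportive only. If the sponsor prefers to keep the fallback, the minimum is a stated criterion together with a ratio of mean totals marginalised over both parts.

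Replace the p<0.20 rule with a short list fixed before analysis, chosen for each endpoint on expected prognostic value from baseline data already collected, for example nicotine dependence, cigarettes per day and quit readiness.

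The cost is wording only, with no new data. The downsides are some loss of efficiency if a zero-inflated model fits better, and that chance imbalances in unlisted covariates are only described.
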